4.2 Primary ITT Analysis Populations

The trial will use an intent-to-treat analysis, and therefore, all randomized participants will contribute to the group they were randomly assigned. For first-stage interventions (MDSF, LAF, RUSF), the analysis population will include all participants who were randomized to a first-stage intervention. For second-stage interventions, the analysis population will include all participants who were randomized to a second-stage intervention (only individuals who recovered during Phase 1).

4.3 Missing Data

We will assume that all outcome data will be missing completely at random, and we will use a complete case analysis (only including those with data for the outcome of interest) as the primary analytic strategy. We will not impute values for any missing outcome data. We will compare the characteristics of people loss to follow-up and those with primary outcome data, we will conduct

a sensitivity analysis using inverse probability weighting (IPW) if there is indication of differential missingness/loss to follow-up by treatment arm (p<0.05).

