5.1 Screening Data

We will report the trial start and end dates for screening as well as the overall number of children screened, the number of screened children and not recruited the reason for non-recruitment, and the number of children enrolled in the trial in a standard trial flow chart. We will also produce a table of these data by study site, which may be considered for a supplemental table in the main trial report.

5.2 Statistical Methods for Primary Outcomes

i. MDSF vs RUSF on 12-week anthropometric recovery (superiority): We will use data from all follow-ups visits up to 12-week visit to define a 12-week anthropometric recovery for each participant. Participants who miss study visits, die, or withdraw from the study will have data from all completed study visits analyzed. If a participant does not complete any follow-up visits at or before the 12-week visit (no follow-up data), they will be excluded from the analysis (complete case). All individuals who have at least 1 follow-up visit will contribute to the analysis. We will not impute missing values for missed visits; the definition of recovery will be based on data available from visits at or before 12 weeks.

We will report the proportion of participants who reached 12-week anthropometric recovery by intervention arm. We will use a log-binomial regression model to present the relative risk (RR) of 12-week anthropometric recovery for the MDSF arm as compared to the RUSF arm. Due to stratified randomization by study site, we will include a fixed effect for the study site in the model. We will present the relative risk, two-sided 97.5% confidence intervals, and a p-value <0.025 will be considered statistically significant (to account for multiple comparisons).

ii. LAF vs RUSF on 12-week anthropometric recovery (non-inferiority): This comparison assesses first-stage randomization options. We will use data from all completed follow-up visits before and at the 12-week visit to define a 12-week anthropometric recovery for each participant. Participants who miss study visits, die, or withdraw from the study will have data from all completed study visits analyzed. If a participant does not complete any follow-up visits at or before the 12-week visit (no follow-up data), they will be excluded from the analysis (complete case). We will not impute missing values for missed visits; the definition of recovery will be based on data available from visits at or before 12 weeks.

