We will report the proportion of participants who reached 12-week anthropometric recovery by LAF and RUSF arms. We will use generalized linear models with a binomial distribution and identity link function to produce risk difference estimates for the LAF arm compared to the RUSF arm. Due to stratified randomization by study site, we will include a fixed effect for the study site in the model. The lower bound of the one-sided 97.5% confidence interval (to account for multiple comparisons) of the risk difference arm will be compared with the prespecified noninferiority margin of -5% to assess non-inferiority. We will also present a p-value for non-inferiority, with a p-value <0.025 considered statistically significant. Two-sided 95% confidence intervals will be presented, which have an upper boundary equivalent to a one-sided 97.5% confidence interval.

iii. MDSF vs RUSF on 24-week sustained anthropometric recovery (superiority): This analysis will utilize data from visits during the first 12 weeks in addition to the 24-week visit. Sustained anthropometric recovery is defined by 12-week anthropometric recovery and continued recovery at the 24-week visit.

If a participant does not complete any follow-up visits at or before the 12-week visit (no 12-week follow-up data), they will be excluded from the analysis (complete case). Individuals who reached anthropometric recovery at 12 weeks but do not have anthropometric data at 24 weeks (loss to follow-up/missing data, death, withdrawal) will also be excluded from the analysis (complete case). Individuals who did not reach anthropometric recovery by 12 weeks will be analyzed as not having met 24-week sustained recovery, regardless of completion of the 24-week visit, as by definition, they will not have met sustained recovery.

We will report the proportion of participants who reached sustained anthropometric recovery at 24 weeks by intervention arm. We will use a log-binomial regression model to present the relative risk (RR) of 24-week sustained anthropometric recovery for the MDSF arm compared to the RUSF arm. Due to stratified randomization by study site, we will include a fixed effect for the study site in the model. We will present the relative risk, 97.5% confidence intervals, and a p-value <0.025 will be considered statistically significant (to account for multiple comparisons).

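### The only missing-data sensitivity analysis runs only if loss differs by arm at p<0.05, and the missing-completely-at-random assumption conflicts with the SAP's own 24-week exclusion rule

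*SAP*

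**What the plan says.** Section 4.3 sets one rule for every outcome: "We will assume that all outcome data will be missing completely at random, and we will use a complete case analysis". It adds "We will not impute values for any missing outcome data".

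Two checks follow. The first is unconditional: "We will compare the characteristics of people loss to follow-up and those with primary outcome data". No analysis is attached to what it finds. The second is conditional: "a sensitivity analysis using inverse probability weighting (IPW) if there is indication of differential missingness/loss to follow-up by treatment arm (p<0.05".

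Section 5.2 then fixes who is missing.
- **12 weeks (items i and ii):** "If a participant does not complete any follow-up visits at or before the 12-week visit (no follow-up data), they will be excluded from the analysis". Children with partial follow-up stay in; item i says "All individuals who have at least 1 follow-up visit will contribute to the analysis".
- **24 weeks, first stage (items iii and iv):** children who recovered by week 12 but have no 24-week measurement are dropped, with the reasons listed as "loss to follow-up/missing data, death, withdrawal) will also be excluded from the analysis (complete case". Children who did not recover by week 12 are kept as failures whether or not they attend at 24 weeks.
- **24 weeks, second stage (item v):** every child has already recovered, so the outcome rests on the 24-week visit alone, and the general rule of section 4.3 applies.

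No other section addresses missing outcomes. Section 5.4 deals with baseline imbalance, and the per-protocol set in section 5.5 again requires non-missing data.

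**The concern.** There are two separate problems.

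First, the assumption does not fit the exclusion rule. Under items iii and iv, once a child has any follow-up visit, whether the 24-week outcome can be missing depends on week-12 recovery, which is itself a component of that outcome. Deaths after recovery go into the same excluded group.

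Second, the gate asks a question that does not settle the matter. Complete-case bias depends on which children are lost in each arm. The gate asks for "if there is indication of differential missingness/loss to follow-up by treatment arm (p<0.05"), which is most naturally read as a test of how much loss there is in each arm. Similar amounts of loss for different reasons would pass it. The trial is open-label, and in Phase 2 one arm receives a package with monthly counselling while the other receives no additional intervention (section 3.1), so reasons for loss that differ by arm are plausible. A non-significant result could then be read as support for an assumption it cannot test.

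At stake are the three 24-week primary comparisons and the changes in anthropometry to 12 and 24 weeks, which could be reported with no missing-data sensitivity analysis.

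**Working it through.** **Inputs from SAP section 3.3.** 2,120 per first-stage arm; 60% recovery by week 12; 40% of recoverers sustain it, so 24% overall in RUSF; 10% loss at 24 weeks; α = 0.025; detectable relative risk 1.21. For the second stage: 45% sustained under standard care, 5% loss, relative risk 1.15.

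**The plan's own figure.** 24% against 24% × 1.21 = 29.04%, with 2,120 × 0.90 = 1,908 per arm and two-sided α = 0.025, gives 90.1% power. The stated 90% is reproduced. The detectable difference is 29.04 − 24 = 5.04 points.

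**How often the trigger fires.** For true loss rates a and b, power ≈ Φ(|b − a|/SE − 1.96), with SE = √{[a(1 − a) + b(1 − b)]/2,120}.
- 5% vs 6%: SE = √(0.1039/2,120) = 0.0070; Φ(1.43 − 1.96) = 30%.
- 5% vs 7%: 78%.
- 10% vs 11%: 18%.
- 10% vs 12%: SE = √(0.1956/2,120) = 0.0096; Φ(2.08 − 1.96) = 55%.
- Equal true rates: 5%, by chance.

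At 1,272 per arm, the second-stage figure in section 3.3, 5% vs 6% gives 20% and 5% vs 7% gives 57%.

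**Fraction excluded at 24 weeks.** Only recoverers can be dropped once a child has a visit. With 10% loss among recoverers, l = 0.60 × 0.10 = 0.06 of the arm, plus any child with no visit at all.

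**Bias in the first-stage risk difference.** Let p be the true sustained-recovery rate in an arm and q the share of excluded children who would have sustained recovery. The observed rate is (p − l·q)/(1 − l). With equal p and equal l in both arms, the observed difference is l × (gap in q)/(1 − l). The gap is an assumption; the SAP gives no figure.
- Gap 10 points: 0.06 × 0.10/0.94 = 0.64 points; 0.64/5.04 = 13%.
- Gap 20 points: 0.06 × 0.20/0.94 = 1.28 points; 1.28/5.04 = 25%.
- Gap 0, for example q = 0.40 in both arms: (0.24 − 0.024)/0.94 = 23.0% in each, so the difference is 0 and the relative risk is 1.00.

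**Effect on the test.** Take no true effect (24% in both arms), l = 0.06, q = 0.50 in RUSF and 0.30 in the comparator. The observed rates are (0.24 − 0.030)/0.94 = 22.3% and (0.24 − 0.018)/0.94 = 23.6%, a relative risk of 1.06. With 2,120 × 0.94 ≈ 1,993 per arm, SE = 0.0133, and the chance of a significant result favouring the comparator is Φ(0.0128/0.0133 − 2.24) ≈ 10%, against a nominal 1.25% in that direction. The true loss rates are equal here, so the trigger would stay silent in about 95% of trials.

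**Second stage.** Every child is a recoverer, so l is the full 5%. The same gaps give 0.05 × 0.10/0.95 = 0.5 and 0.05 × 0.20/0.95 = 1.1 points, or 8% to 16% of the detectable 45% × 0.15 = 6.75 points.

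**The case against.** Much of the case on the other side stands, and it limits the point.

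- **Loss is examined to some degree.** A reader might infer that outcome-related loss is never looked at. Section 4.3 does plan an unconditional comparison of lost and observed children. What is missing is any re-analysis that follows from it.
- **The trigger wording does not say rate.** A broader reading is possible, but the text names no other test.
- **A larger bias is tempting.** Applying 10% loss to the whole arm gives 0.10 × 0.10/0.90 = 1.1 to 0.10 × 0.20/0.90 = 2.2 points (22% to 44% of 5.04). Under the exclusion rule this would need 0.10/0.60, or about 17%, loss among recoverers.
- **The fall from 24.0% to 23.0% under purely random loss among recoverers is not bias in the comparison.** It affects both arms alike. It shows only that the assumption does not match the rule.
- **The 12-week primary comparisons are little exposed.** Measurement is weekly and only children with no visit are dropped.
- **The change outcomes need less than missing completely at random.** With a correctly specified model, complete-case ANCOVA adjusted for baseline value and site (section 5.3) stays valid if loss depends only on arm, site and baseline value. It does not cover loss related to later measurements.
- **IPW is not a full answer.** It removes only bias explained by the variables in the weights, and it should not make survivors stand in for children who died.

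**Conclusion.** The point holds in a limited form. The missing-completely-at-random statement conflicts with the 24-week rule in section 5.2 iii and iv. The only re-analysis depends on a significance test that cannot show whether complete-case estimates are biased and that often misses real differences in loss.

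Under no true effect, 10% loss among recoverers and an assumed gap of 10 to 20 points among lost children, the first-stage 24-week risk difference is off by about 0.6 to 1.3 points, 13% to 25% of the detectable difference. Both the loss among recoverers and the gap are assumptions. If lost children have the same outcomes in both arms and there is no true effect, there is no bias.

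The SAP does not support the stronger conclusion that the primary results will be biased, or that complete case is unusable as the headline. This is an improvement that should be made before analysis, not a fatal flaw.

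**What to change.** 1. Delete the p<0.05 condition in section 4.3. Always report IPW as a sensitivity analysis for the three 24-week primary comparisons and the anthropometric change outcomes.
2. Build the weights from arm, site, age, sex, and baseline WLZ and MUAC, adding week-12 WLZ and MUAC for the 24-week outcomes.
3. Replace the missing-completely-at-random statement with missing at random given these variables for the weighted analysis. Keep complete case as the headline result.
4. Because IPW cannot address loss that depends on the unseen outcome, add a delta-adjusted (tipping-point) analysis for the 24-week primary comparisons.
5. Treat the counting of deaths after recovery as a separate endpoint question and settle it in the outcome definition. IPW does not resolve it.

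The cost is a change of SAP wording, modest programming with variables the trial already collects, and one more set of results to report.

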4.4 Multiple Testing

We have adjusted for multiple testing for primary outcomes of the same randomization stage and outcome. For 12-week anthropometric recovery for first-stage randomization interventions, we will make two primary comparisons: MDSF vs RUSF and LAF vs RUSF. As a result, we used a Bonferroni correction and assumed an α =0.025 (0.05/2) in sample size calculations, and we will consider a p-value <0.025 as statistically significant. For 24-week sustained anthropometric recovery for first-stage randomization interventions, we will make two primary comparisons: MDSF vs RUSF and LAF vs RUSF. As a result, we used a Bonferroni correction and assumed an α =0.025 (0.05/2) in sample size calculations, and we will consider a p-value <0.025 as statistically significant. There is only one test of the second-stage randomization intervention, and therefore no correction for multiple testing will be applied and an α =0.05 is used in sample size calculations, and we will consider a p-value <0.05 as statistically significant.

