Based on assumptions of 1:1 randomization, 90% power, a one-sided α =0.025 (0.05/2 for multiple comparisons), 5% loss to follow-up/missing data, and that 60% of participants would have 12-week anthropometric recovery outcome in the RUSF and LAF arms, we would require 2,120 participants in each intervention group. As the rate-limiting randomization #1 sample size, the trial 2,120 participants are enrolled in each of the three first-stage randomization interventions, totaling 6,360 total participants in the trial.

Primary Comparison #2: MDSF vs RUSF on 12-week anthropometric recovery (**superiority**): This hypothesis is based on the evidence from a proof-of-principle study conducted in Bangladesh, which showed that MDSF is better than RUSF in promoting growth. We anticipate that 60% of enrolled children will achieve anthropometric recovery within 12 weeks of enrolment in the RUSF group (comparison group). Based on an enrollment of 2,120 per intervention arm, 1:1 randomization, an α of 0.025 (0.05/2 due to multiple comparisons), and 5% loss to follow-up/missing data, we will have 90% power to detect a relative risk of 1.09 for 12-week anthropometric recovery for MSDF as compared to RUSF.

Primary Comparison #3 MDSF vs RUSF on 24-week sustained anthropometric recovery (superiority): This hypothesis is also based on the evidence from a proof-of-principle study conducted in Bangladesh, which showed that MDSF is better than RUSF in promoting growth.

We anticipate that 40% of enrolled children in the second randomization, therefore 24% overall will achieve 24-week sustained anthropometric recovery in the RUSF group (comparison group). Based on an enrollment of 2,120 per arm, 1:1 randomization, an α of 0.025 (0.05 / 2 due to multiple comparisons), and 10% loss to follow-up/missing data, we will have 90% power to detect a relative risk of 1.21 for 24-week sustained anthropometric recovery for MSDF as compared to RUSF.

Primary Comparison #4 LAF vs RUSF on 24-week sustained anthropometric recovery (**superiority**): We believe that the LAF group could have more sustained recovery than RUSF because it has higher acceptability, lower likelihood of displacing usual diet and breastfeeding, and an easier transition to giving adequate home foods to the child in phase 2 after recovery has been achieved.

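### For the two 24-week first-stage superiority tests, Holm would replace plain Bonferroni at no cost in family error and add about 3 points of power per test if both foods have RR 1.21: a cheap improvement, not an error

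*SAP*

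**What the plan says.** SAP 4.4 (Multiple Testing) defines the family: "For 24-week sustained anthropometric recovery for first-stage randomization interventions, we will make two primary comparisons: MDSF vs RUSF and LAF vs RUSF". It continues: "As a result, we used a Bonferroni correction", with 0.05/2 = 0.025 per test also taken into the sample size, and sets the decision rule: "we will consider a p-value <0.025 as statistically significant". The correction is described once for the 12-week pair and once for the 24-week pair; this point concerns only the second.

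SAP 5.2 iii (MDSF) and iv (LAF) repeat the rule for each test: "We will present the relative risk, 97.5% confidence intervals, and a p-value <0.025 will be considered statistically significant". No step-down, hierarchical or alpha-recycling rule appears anywhere in the SAP.

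SAP 3.3 gives the planning assumptions for both comparisons: "therefore 24% overall will achieve 24-week sustained anthropometric recovery in the RUSF group", 2,120 per arm, 10% loss, and 90% power for a relative risk of 1.21. SAP 4.1 hypothesises superiority at 24 weeks for each of the two foods.

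**The concern.** Under the plan, the threshold for one food ignores the result for the other. Suppose MDSF is clearly superior to RUSF and LAF has p = 0.03. The plan declares LAF not significant. Yet once the MDSF null has been rejected at 0.025, only one hypothesis in the family is left, and testing it at the full 0.05 keeps the family error at or below 0.05. Holm's procedure does exactly this, under any dependence between the tests.

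At stake is some power for the second of two primary comparisons, in the situation the SAP itself hypothesises, where both foods are better than RUSF at 24 weeks.

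**Working it through.** **Inputs.** From SAP 3.3: RUSF rate 24%, 2,120 per arm, 10% loss, relative risk 1.21. So evaluable n = 2,120 × 0.90 = 1,908 per arm, and the supplemented rate is 0.24 × 1.21 = 0.2904. The level is 0.025 per test (3.3 and 4.4). The SAP does not state sidedness for the 24-week tests. I take two-sided, because 5.2 i gives "two-sided 97.5% confidence intervals, and a p-value <0.025 will be considered statistically significant" for the parallel 12-week superiority test, and because only this reading reproduces the stated power.

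**The plan's own figure.** The difference is 0.2904 − 0.24 = 0.0504 and the mean rate is 0.2652.

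- SE under the null: √(2 × 0.2652 × 0.7348 / 1,908) = 0.01429
- SE under the alternative: √((0.24 × 0.76 + 0.2904 × 0.7096) / 1,908) = 0.01427
- Power: Φ((0.0504 − 2.2414 × 0.01429) / 0.01427) = Φ(1.287) = 90.1%

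The stated 90% reproduces. The required n is 1,902 evaluable, or 1,902 / 0.90 = 2,114 enrolled, against 2,120 planned. A one-sided 0.025 test would give 94.2%.

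**Holm, both foods at RR 1.21.** The two statistics share the RUSF arm. Their correlation is about 0.24 × 0.76 / (0.24 × 0.76 + 0.2904 × 0.7096) = 0.47, and I used 0.47 to 0.5. Each statistic has mean about 2.241 + 1.287 = 3.53. The critical values are 2.241 (two-sided 0.025) and 1.960 (two-sided 0.05). At correlation 0.47:

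- P(both exceed 2.241) = 83.2%: both shown under Bonferroni
- P(a given one exceeds 2.241 and the other exceeds 1.960) = 86.3%
- Holm power per test = 90.1 + 86.3 − 83.2 = 93.2%
- Holm, both shown = 2 × 86.3 − 83.2 = 89.4%

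Simulated three-arm trials (1,000,000, with 1,908 per arm) agree and also cover the other cases:

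| True relative risks | Quantity | Bonferroni | Holm |
|---|---|---|---|
| 1.21 and 1.21 | each test | 90.1% | 93.2% |
| 1.21 and 1.21 | both shown | 83.5% | 89.5% |
| 1.21 and 1.21 | at least one shown | 96.9% | 96.9% |
| 1.21 and 1.12 | weaker food's test | about 42% | about 53% |
| 1.21 and 1.00 | effective food's test | about 90% | gain of 0.1 to 0.2 points |
| 1.21 and 1.00 | ineffective food declared different (two-sided) | 2.5% | about 4.5% |
| 1.00 and 1.00 | family error | 4.6% | 4.6% |

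The pair 1.21 and 1.12 is my illustration of unequal effects; 1.12 is not an SAP figure. The probability of at least one rejection is identical in every row, because both methods start by testing the smaller p at 0.025.

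**The case against.** The strongest reply is that nothing here is wrong. Bonferroni is valid, prespecified and used consistently in 3.3, 4.4 and 5.2. The planned 90% power is met with it, and each 97.5% interval agrees with its test. That stands, and it is why this is an improvement and not an error.

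Three further objections also stand in part:

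- **The gain is conditional.** RR 1.21 is what each comparison can detect with 90% power; it is not a forecast that both foods reach it. A reader might infer that every 24-week test loses 3 points whatever the truth. The documents do not support that: if only one food works, it gains nothing material.
- **Showing both effects is not a stated objective.** SAP 4.1 has a separate hypothesis for each food. The 6-point figure is therefore supplementary; the per-test figure is the one to weigh.
- **There is a price in false claims.** The same error control refers to the guaranteed 5% ceiling. Below it, the error for an ineffective food rises from 2.5% to about 4.5% when the other food works.

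One might add that the interim looks in 4.6 use up error that Bonferroni's slack would absorb. At p<0.001, each look adds at most 0.1 point to the error of a given test, under either method, so this does not separate them in practice.

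It is also tempting to say that the trial wastes participants already enrolled for these tests. SAP 3.3 says otherwise: the sample size was set by the 12-week non-inferiority comparison.

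**Conclusion.** The point holds as a cheap efficiency gain. For the 24-week pair, Holm keeps the SAP's 0.05 family level, rejects everything that plain Bonferroni rejects, and needs no added assumption about how the tests are correlated. If both foods have RR 1.21, it adds about 3 points of power per test and about 6 points to the chance of showing both. With unequal effects the benefit goes mainly to the weaker food (about 11 points at RR 1.12). With one effective food there is no material gain.

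These sizes rest on 24% in RUSF, 1,908 evaluable per arm, two-sided tests and the shared control arm. They do not show that the planned analysis is invalid or that the 24-week tests are underpowered; neither is so. Nor do they carry over to the 12-week pair, which mixes a non-inferiority test with a superiority test and would need its own argument.

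**What to change.** In SAP 4.4 (24-week sentences) and 5.2 iii-iv, replace the fixed threshold by Holm for this pair. Suggested wording: the smaller of the two two-sided p-values is tested at 0.025; if it is met, the other is tested at 0.05; otherwise testing stops and neither food is declared superior. State in 5.2 iii-iv that the tests are two-sided.

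Keep the 97.5% intervals, and print the 95% interval beside them for a food declared at the second step.

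The SAP should state two costs. A food declared at the 0.05 step may have a 97.5% interval that includes 1. And when only one food works, the false-claim rate for the other rises from 2.5% to about 4.5%, within the 5% family level.

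The change is to wording only. It needs no participants, visits or data, and leaves the sample size and the interim boundary in 4.6 alone. It must be fixed before unblinding. Leave the 12-week tests as they are.
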